Reasons for study withdrawal may include the following:

- Adverse event
- Non-compliance with protocol/protocol deviation
- Sponsor's decision
- Lost to follow up
- Withdrawal of consent

Subjects who are withdrawn or terminate early from the study will be replaced under certain circumstances. These circumstances are withdrawal prior to the completion of all three blood and synovial fluid draws (the study is powered to show a difference in these markers and will be underpowered if these subjects cannot be replaced)

The date and reason must be recorded for all subjects who withdraw from the study. If the reason for withdrawal is a treatment-emergent AE, the specific AE will be identified on the CRF and every attempt will be made to follow the event until resolution.

In addition, every attempt should be made to complete the Visit 6/Early Termination assessments.

If a subject discontinues the study for any reason prior to Visit #5/12-14 weeks post injury visit, then the collected data will be included in the safety analysis, however will not be included in the overall efficacy analysis and a replacement subject will be enrolled in the study.

STUDY PROCEDURES/EXAMINATIONS (See Appendix A)

Demographics, medical history and medication history: Demographic data to be collected on screening visit will include height, weight, date of birth, age, gender and race. Detailed past medical history and medication history will be collected on screening visit. The medical history or concurrent medication history will be noted on each visit.

Knee Aspiration: All subjects undergo knee aspiration to dryness at initial encounter (1-4 days after ACL injury), (+/- 4 days), 12-14 days after injury, at the time of surgery. Should a subject be enrolled into the study and choose not to undergo ACL reconstruction, subject will received treatment according to this protocol but, aspiration at time of surgery will be omitted. Planned aspiration postoperatively will not be performed unless clinically necessary for significant postoperative effusions. If an aspiration is done, a sample will be retained for analysis.

Visit 1 Screening (1-4 days post injury) (+/- 4 days): Upon arriving at the study clinic potential subjects will have the following assessments: range of motion, knee instability

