but are not limited to severe post-administration pain requiring treatment, infection of the injection site or the knee joint, ER visit following the administration of the study drug at visit 1 or 2. Due to the short half life of the drug we do not expect any SAE's related to the drug administration later than after the date of ACL surgery. During the observation time (time of surgery to 6 months post-op) other, non-drug related, SAEs may occur which will be recorded and reported.

Any reported SAE occurring during the study must be reported by the sponsor to the Food and Drug Administration and the appropriate Institutional Review Board. Any SAE due to any cause, whether or not related to the study drug, must be reported within 24 hours of when the Investigator becomes aware of the event. Investigators who need to report SAEs to the sponsor may do so by utilizing FDA Form 3500A the sponsor provided SAE reporting form and faxing report to [contact].

Plan for unexpected adverse event (AE) reporting. Serious AEs will be reported to Human Subjects/IRB within 48 hr. Unanticipated events will be reported to the IRB.

Monitoring of adverse events. Adverse events will be monitored via exams, vital signs, review of subject's medical chart, and documented. Each visit will be documented with a progress note in the research chart.

Adverse Event Follow-up

All AEs, including clinically significant changes in physical examinations findings, or isolated clinically significant laboratory findings must be followed until the event resolves, the condition stabilizes, the event is otherwise explained, or the subject is lost to follow-up. If resolved or stabilized, a resolution date should be documented on the CRF.

Adverse events ongoing at the final visit or early termination visit will be followed until that adverse event is resolved.

Potential Risk:

Safety Precautions: Participants will be followed at regular intervals by their study doctor. On each visit participants will be evaluated for adverse events according to GCP guidelines and reported accordingly to IRB and FDA regulations.

Benefit Vs Risk: Triamcinolone is a first line treatment of established OA. In this trial, we expect that an early intervention with Triamcinolone may block the deleterious cascade of joint degradation events after joint injury. We expect a significant effect of Triamcinolone on post-injury pain and concomitantly an increased improvement in early function.

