Sample Size and Power Analysis - We used the VAS and WOMAC data from Chevalier et al. as the template for power calculations [4] and the change in KOOS pain and ADL from our study. Chevalier reported a 53% response rate by VAS. Response was defined as a 50% improvement in VAS pain score from baseline. We observed comparable differences in our study (20-30% between outcomes in the IL-1Ra and placebo groups); therefore this dataset is reasonable to estimate study power. Based upon the change in VAS pain score in the Chevalier study, and conservatively estimating a placebo response rate of 30%, the effect size was 0.47 for a dichotomous outcome. At this effect size power for a sample size of 17/group is reasonable (65%) for the weakest possible outcome (i.e., one that only generates a "yes" or a "no" for each patient). Moreover, power is excellent for the continuous KOOS outcomes. With 17 patients per group we achieve 90% power for effect sizes of approximately 0.77 and 80% power for effect sizes of approximately 0.65. These latter effect sizes are in standard deviation multiples. So, for example, if the standard deviation of the VAS is approximately 20, and we expect an improvement of approximately 20 units in the intervention group, we can tolerate an improvement of approximately 7 units in the placebo group and still have 90% power (i.e. the effect size is $(20-7)/20 = 0.65$). Moreover, using the effect size standard benchmarks of 0.50 as moderate and 0.80 as large, we will be powered to detect moderate-to-large effects of the intervention, which is consistent with intuition for a study of this size. Power calculations based on our pilot KOOS data confirm this estimate. The change in KOOS (days 0-4) comparing treatment and placebo groups yielded an effect size of 0.62 for pain and 1.08 for ADL. At a

group size of 17 we will have 80% power to detect a difference in KOOS pain and >99% power to detect a difference in KOOS ADL.

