The power calculations include several caveats. The power calculation was performed based upon the use of a IL-1 receptor antagonist. There is no clinical data available in a young patient population with knee ligament injuries regarding their pain improvement after cortisone injection. The IL1RA data is the most comparable. Cortisone is a wider spectrum anti-inflammatory than IL-1RA and thus may have a larger effect on pain control that may be longer lasting. In that case our study may be over-powered. First, for purposes of power calculation, we have not assumed a full repeated measures analysis, but have instead analyzed change from baseline at a single time point. Second, we note that in trials such as this, the power of a non-parametric analysis is never much lower than its parametric analog (the "asymptotic relative efficiency" of the Wilcoxon test is at least 0.95), leading us to conclude that our parametrically based power calculations should apply with equal force to a non-parametric analysis.

Statistical analyses - Results from a sample of this size may not be normally distributed. Therefore, non-parametric statistical measures may be used. Primary outcome measures evaluating for change in KOOS and IKDC will be assessed at multiple points and will be analyzed for change between groups using Friedman two-way ANOVA for repeated measures. Synovial fluid analyses comparing the three groups at three time points will be analyzed using the Wilcoxon Signed Rank Sum Test with Hochberg corrections for multiple time points. Alternatively, if results are normally distributed or can be transformed (e.g., by log transformation) to meet the criteria for normality for parametric analysis, then repeated measures ANOVA will be utilized comparing treatment groups. P-values of less than or equal to 0.05 will be considered statistically significant. For those subjects enrolled in the extended follow-up sub-study the 24 month time point will be examined as an additional time point. Additionally, correlation analyses will be used to examine the relationship between biomarkers collected at Visits 1-3 and KOOS and IKDC values and MRI findings at 24 month follow-up.

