The principal investigator will permit the Sponsor's personnel (or designees) to audit all CRF/eCRFs and supporting documentation, eg, hospital, office, clinic, pharmacy, and laboratory records for each subject. The principal investigator agrees to cooperate with the Monitor to ensure that any problems detected in the course of these monitoring visits are resolved. In accordance with the ICH, GCP and the Sponsor and/or its designee audit plans, this study may be selected for audit. Inspection of site facilities (eg, pharmacy, drug storage areas, laboratories, etc.) and review of study-related records will occur in order to evaluate the study conduct and compliance with the protocol, ICH GCP, and applicable regulatory requirements.

Data Safety Monitoring Board

Monitoring for adverse events will be conducted in real-time by the study investigators and study coordinators. Risks involved with this study are considered greater than minimal risk. For this reason, we will utilize the standing independent Data Safety Monitoring Board (DSMB) as chartered by the University of Kentucky Center for Clinical and Translations Science (CCTS). The DSMB will meet semiannually or as needed, and will review subject recruitment, AE's, side effects, laboratory results, dropouts, protocol violations, and inclusion/exclusion criteria. More frequent meetings will take place if side effects or other problems are prevalent.

Study Stopping Criteria

- local intolerance of the administered Kenalog® or any sign of allergic response.
- development of signs and symptoms before the second time point preventing the second administration of the study drug.
- Any patient reported SAE after the first or second administration of the study drug.
- Diagnosis with any condition as outlined in the exclusion criteria during the course of the initial 2 weeks of study enrollment.

Data Recording and Record Retention

The PI must maintain all Essential Documents (as listed in the ICH Guideline for GCP) until notified by the Sponsor and in accordance with all local laws regarding retention of records.

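### Randomised, dosed subjects who leave before Visit 5 are dropped from the efficacy analysis and replaced, and no analysis of everyone randomised is planned

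*Combined protocol and SAP*

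**What the plan says.** The file holds three copies of the protocol, and the rule is the same in each. Early Termination of Subjects from Study sets the condition, "If a subject discontinues the study for any reason prior to Visit #5/12-14 weeks post injury visit", and the consequence: data go to the safety analysis, "however will not be included in the overall efficacy analysis and a replacement subject will be enrolled in the study". The same section asks that "every attempt should be made to complete the Visit 6/Early Termination assessments".

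That section also gives a narrower replacement rule: "These circumstances are withdrawal prior to the completion of all three blood and synovial fluid draws (the study is powered to show a difference" in the markers). The third draw is on the day of surgery, Visit 3. Sample Size and Power Analysis, however, works only from VAS response and KOOS, for example "The change in KOOS (days 0-4) comparing treatment and placebo groups yielded an effect size of 0.62 for pain and 1.08 for ADL".

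Adverse event is one of the listed withdrawal reasons, and the Adverse Events section names "severe post-administration pain requiring treatment, infection of the injection site or the knee joint" among such events. Study Stopping Criteria lists "Any patient reported SAE after the first or second administration of the study drug" without saying whether meeting it ends dosing, participation or the trial.

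Under Statistical analyses, change in KOOS and IKDC "will be analyzed for change between groups using Friedman two-way ANOVA for repeated measures", with repeated measures ANOVA as the parametric alternative. The plan does not define an analysis population beyond the exclusion rule, a method for missing values or a sensitivity analysis.

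**The concern.** Randomisation makes the arms comparable as allocated. Once membership of the analysed groups depends on something that happens after the first injection, that protection is lost. Replacement restores the count of 17 per group but not the comparability.

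If leaving is related to pain and differs by arm, the comparison of drug with placebo is biased. Either direction is possible: removing subjects who tolerate the drug poorly flatters it, and removing placebo subjects with uncontrolled pain works against it. Blinding does not prevent this, because a blinded patient can still leave because of pain. Values already collected from these subjects, such as KOOS and IKDC at Visits 2 to 4, are set aside for efficacy, and so are the early-termination assessments that the protocol works to obtain.

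**Working it through.** **Order of events.** Randomisation and first injection: Visit 1. Second injection: Visit 2, 12–14 days after injury. Surgery and third draw: Visit 3. Visit 5: 4–6 weeks after surgery in the visit schedule, but tied to 12–14 weeks after injury in the exclusion rule. Every reading of the cut-off falls after the first injection.

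**The two replacement triggers.** Someone who leaves between Visit 3 and Visit 5 has given all three draws. The first trigger does not replace that person; the second does.

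**Inputs from the documents.** 17 per group; significance at 0.05 (sidedness not stated; two-sided assumed here). The yardstick is the VAS example in the power section: (20 − 7)/20 = 0.65 SD.

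**The plan's own power figure.** It states 80% power at 0.65 SD with 17 per group. For two groups and a two-sided test, power = Φ(0.65 × √(17/2) − 1.96) = Φ(−0.065) = 47%. The stated figure is not reproduced. That is a separate matter, and nothing below depends on it.

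**Assumptions.** No discontinuation rate is given, so I take m = 1, 2 or 3 of 17 leaving one arm. There is no true effect, outcomes are normal with SD 1, and each leaver is replaced by a fresh draw. The test is a two-sample t-test at one time point, with 40,000 simulated trials per setting.

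| How subjects leave | Type I error, m = 1 / 2 / 3 | Bias (SD), m = 1 / 2 / 3 |
|---|---|---|
| One arm, unrelated to outcome | 4.8 / 5.0 / 5.1% | 0 |
| One arm, odds double per SD worse | 5.1 / 5.6 / 6.4% | 0.04 / 0.07 / 0.10 |
| One arm, poorest scorers leave | 7.0 / 9.9 / 13.1% | 0.11 / 0.18 / 0.24 |
| Both arms, poorest scorers leave | 6.7 / 7.8 / 8.4% | 0 |

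Repeat runs agree to within about 0.5 percentage points.

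**Closed-form check of the worst case.** Replacing the m lowest of 17 by average draws shifts the arm mean by minus the sum of their expected values, divided by 17. The three lowest expected normal order statistics are −1.794, −1.319 and −1.029:

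- m = 1: 1.794/17 = 0.106
- m = 2: (1.794 + 1.319)/17 = 0.183
- m = 3: (1.794 + 1.319 + 1.029)/17 = 0.244

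Against 0.65 SD these are 16, 28 and 38%. For the graded case, 0.039, 0.073 and 0.101 SD are 6, 11 and 16%.

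**A second model.** Suppose a fraction q of one arm would leave, replacements are subject to the same selection, and leaving correlates ρ with outcome. Then bias = ρφ(z_q)/(1 − q). At q = 0.12 (2 of 17) and ρ = 1 this is 0.200/0.88 = 0.23 SD, with type I error about 10%; at ρ = 0.5 it is 0.11 SD and about 6%. Over q = 0.06 to 0.18 and ρ = 0.5 to 1, bias runs from 0.06 to 0.32 SD. When both arms lose subjects alike under this model, type I error stays near 5% (4.9% at q = 0.12, 5.3% at q = 0.24). The both-arms inflation in the table therefore depends on the model.

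**Does the remedy work?** Take two visits with an assumed correlation of 0.6 and leaving driven by the observed Visit 2 score (20,000 trials). At the later visit, exclude-and-replace gives bias of 0.02 / 0.04 / 0.06 SD (odds double) and 0.07 / 0.11 / 0.15 SD (poorest leave). A likelihood analysis of everyone randomised plus replacements gives at most 0.003 SD in absolute value. If the poorest scorers leave before Visit 2, with only baseline observed, the likelihood analysis still carries 0.11–0.23 SD at a baseline correlation of 0.3 and 0.07–0.17 SD at 0.6. Exclude-and-replace carries 0.11–0.25 SD.

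**The case against.** The strongest reply is that the size is entirely assumed. The documents give no discontinuation rate and no sign that it will differ by arm. The graded scenario barely moves the type I error, and when both arms lose subjects that way it is 5.4–5.6% with no mean bias. The 13% figure needs the three poorest scorers of 17 to leave, all from one arm. The simulations use a single-time-point t-test, not the planned repeated-measures tests. All of this stands, and it is why no single inflation figure should be quoted as the trial's own.

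The link to pain is also possible rather than shown. The protocol does not say that severe injection pain ends participation, and both arms have aspiration and a blinded 10 ml injection. This makes differential leaving less likely but does not rule it out.

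The cut-off is unclear: 12–14 days after injury is Visit 2, so the reference to weeks may be a slip. If Visit 2 was meant, the loss of Visit 2–4 questionnaires and the conflict between replacement triggers after Visit 3 would fall away; the selection after dosing would not. It is likewise an inference that the excluded subjects' fluid data are lost, since the rule refers to overall efficacy and does not mention the biomarker analysis.

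The mixed model is shown at its best when leaving depends on observed scores. That criticism stands: for pain-driven losses before Visit 2 it leaves much of the bias.

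Finally, the trial is meant to supply preliminary data for a larger one. That lowers the stakes of a single p-value, but a biased estimate would carry into that trial's planning.

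**Conclusion.** The concern holds and should be fixed before the analysis. The rule is explicit, it acts after dosing, the protocol's own adverse-event wording allows it to depend on pain, and nothing in the plan offsets it or would reveal its effect. Confidence is high on those points.

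The size and direction are not known. For 1 to 3 leavers of 17 in one arm, the bias ranges from nil to 0.24 SD (up to 0.32 SD under the second model). The lower end applies if leaving is unrelated to outcome, the upper end only if the poorest scorers are the ones who leave. Related to the 0.65 SD in the plan's own example, 0.24 SD is 38%. With 17 per arm, a few subjects are enough to matter.

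**What to change.** - Define the primary efficacy set as all randomised subjects in their assigned arm, using every KOOS, IKDC and biomarker value observed up to discontinuation and the early-termination assessments. State which visit an early-termination value counts towards.
- Friedman's test and standard repeated measures ANOVA need complete data. Replace them as the primary method with one that uses partial data, such as a likelihood-based mixed model for repeated measures, on ranks or transformed values if needed.
- Allow replacements as additions only; the subjects they replace stay in the analysis. State how a replacement is allocated.
- Report completers to Visit 5 as a sensitivity analysis. Add another in which leavers' unobserved values are worse than the model predicts, because the mixed model does not cover that case.
- Keep one replacement rule tied to a scheduled visit, say how it applies to subjects who choose no surgery, and reconcile the 12–14 weeks label with the Visit 5 schedule.
- Reconcile Study Stopping Criteria with the early-termination section on what meeting a criterion ends.
- Remove the statement that the study is powered for the markers, or support it with a calculation.

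The cost is protocol and SAP wording and a little more analysis; every assessment needed is already scheduled or sought. There are two drawbacks. The all-randomised estimate may be diluted by subjects who missed the second injection, and some bias remains if leaving depends on values never observed.
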